## ABBREVIATIONS

AE	Adverse event
CA	Competent authority
CE	Conformité Européene
CEC	Clinical events committee
CKD	Chronic kidney disease
CRF	Case report form
EC	Ethical Committee
EFS	Early feasibility study
eCRF	Electronic case report form
ePTFE	Expanded polytetrafluoroethylene
EU	European Union
FDAAA	Food and Drug Administration Amendments Act
GCP	Good clinical practices
GFR	Glomerular filtration rate
ICH	International Conference on Harmonisation
ICU	Intensive Care Unit
ID	Identity Number
IDMJE	International Committee of Medical Journal Editors
MDD	Medical Device Directive
MR	Mitral Regurgitation
NYHA	New York Heart Association
PA	Pulmonary Artery
SAE	Serious Adverse Event
SOC	Standard of Care
TOE	Transoesophageal Echocardiogram
TTE	Transthoracic Echocardiogram
USADE	Unanticipated Serious Adverse Device Effect
WHO	World Health Organisation

## II. STUDY SUMMARY

Title:	Mitral TR ans- A pical Ne o C hordal E cho-guided R epair (TRACER) Trial
Protocol Number:	HMCE -1002-00k
Study Status:	Enrollment was completed as of November 2017. Follow-ups range from 6 to 36 months. The purpose of this amendment is to extend to 5 years of follow-up post-implant.
Design:	This is a prospective, single arm, nonrandomised, multi-center EU study to demonstrate the performance and safety of the Harpoon Medical device in patients with degenerative MR.
Study Duration:	Projected enrollment of first patient: April 2016 Projected exit of final patient: November 2022
Primary Objective:	The primary objective of this study is to evaluate the safety and performance of the Harpoon Medical device.
Patient Population:	Patients with “Severe” mitral regurgitation as a result of posterior leaflet prolapse.
Sample Size:	Up to twenty (20) patients in the UK will be enrolled.
Number of Sites:	Up to eight (8) sites in up to four (4) countries. Each country will enroll up to twenty (20) patients.
Treatments:	Up to eight (8) pairs of ePTFE chordae tendineae may be placed in the posterior leaflet of the mitral valve using the Harpoon Medical Transapical Device in order to establish effective coaptation of the mitral leaflets.
Endpoints:	Performance endpoints:  Primary Performance Endpoints: To demonstrate that the Harpoon Medical device performs as designed and has the ability to successfully implant one or more ePTFE chordae tendineae on the mitral valve via a small left thoracotomy on the beating heart and reduce mitral regurgitation from “severe” to less than or equal to “moderate” at the conclusion of the procedure and at 30 days post-procedure.  Secondary Performance Endpoints: Severity of mitral regurgitation at 6 months, 12 months, 18 months, 24 months, 30 months, and 36 months follow-up shall be tracked and recorded.

### **Safety Goals:**

**Primary Safety Endpoints:** Procedure freedom from Serious Adverse Events (SAEs) during the ePTFE implantation procedure, at discharge, and at 30 days follow-up shall be tracked and recorded.

**Secondary Safety Endpoints** Freedom from Serious Adverse Events (SAEs) at 6 months, 12 months, 18 months, 24 months, 30 months, and 36 months follow-up shall be tracked and recorded.

#### **Inclusion Criteria:**

- Age  $\geq$  18 years
- Patient referred for mitral valve surgery
- Presence of severe MR as read on an echocardiographic study performed within 60 days prior to procedure.
- Estimated post-ePTFE chordae tendineae implantation coaptation surface is adequate in the judgment of the operating surgeon and the patient eligibility committee
- Degenerative mitral valve disease
- Patient is able to sign informed consent and able to return for follow-up and is capable of participating in all testing associated with this clinical investigation
- Women of child-bearing potential have a negative pregnancy test

#### **Exclusion Criteria:**

- Age < 18 years
- Infective endocarditis
- Anterior or bileaflet prolapse
- Functional MR
- History of Mediastinal Radiation
- Inflammatory (rheumatic) valve disease
- Requirement for concomitant cardiac surgery (e.g., coronary artery bypass grafting (CABG), aortic valve surgery, etc.)
- Symptomatic coronary artery disease
- Cardiogenic shock at the time of enrollment
- ST segment elevation myocardial infarction requiring intervention within 30 days prior to enrollment
- Evidence of cirrhosis or hepatic synthetic failure
- Pregnancy at the time of enrollment (women of child bearing age should have negative pregnancy within 14 days of surgery)
- Severe pulmonary hypertension (PA systolic pressure > 70 mmHg)
- Previous cardiac surgery, or surgery on the left pleural space
- Left ventricular, atrial or appendage thrombus
- Severely calcified mitral leaflets
- Recent stroke (< 6 months) with permanent impairment

- EuroScore (for mitral valve repair) > 8%
- Patients with contraindications to Transoesophageal echocardiography
- Severe left or right ventricular dysfunction
- NYHA Class IV
- Renal insufficiency CKD stage 3b or worse (GFR < 45 ml/min/1.73 m^2)
- Patient is participating in another clinical study for which follow-up is currently ongoing. (Co-enrollment in an investigational device or interventional study)
- Patient with non-cardiac co-morbidities and life expectancy < 1 year
- Patient has a condition or conditions that, in the opinion of the Investigator, preclude participation, including willingness to comply with all follow-up procedures

**Follow-up:**

The estimated enrollment period is 24 months, and all patients will have follow-up visits at 30 days, 6 months, 12 months, 18 months 24 months, 30 months, 36 months, 48 months and 60 months after implantation.

### III. INTRODUCTION

#### Mitral Regurgitation, Transapical mitral valve repair, and the Harpoon Medical device

Mitral valve disease is the second common valvular heart disorder requiring surgery in Europe, with nearly 8 million Europeans estimated to have severe mitral valve regurgitation ("MR"). MR results in a volume overload on the left ventricle which in turn leads to ventricular dilation, decreased ejection performance, pulmonary hypertension, symptomatic congestive heart failure, atrial fibrillation, right ventricular dysfunction and death. Successful surgical mitral valve repair restores mitral valve function, abolishes the volume overload on the left ventricle, improves symptom status and prevents adverse left ventricular remodeling.

The large majority of MR results from either degenerative disease (caused by elongated or ruptured native chords that fail to support the mitral valve leaflets) or functional ischemic or idiopathic MR (the motion of the normal mitral valve leaflets is restricted by the enlarged ventricle) both of which lead to ineffective valve closure and regurgitation.

Two-thirds of all Mitral valve procedures in North America are performed on patients with degenerative MR and that percentage is estimated to be similar in the European Union (EU). Open cardiac surgery is a common method of treating degenerative mitral valve regurgitation which involves replacing and/or supplementing elongated or ruptured chords with artificial chords made of ePTFE, a commercially available material which has a 20+ year history of safety in conventional mitral valve repair procedures. While open cardiac surgery has a low mortality risk (less than 1%) and is evidenced to have excellent long term outcomes, it has risks, including stroke, bleeding, infection, and the risk of valve replacement rather than repair. It is anticipated that use of the Harpoon device could achieve similar outcomes while decreasing the invasiveness of mitral valve repair.

#### DEVICE DESCRIPTION

The Harpoon Medical Transapical device is intended to be used to reduce the degree of mitral regurgitation by delivering and anchoring artificial chordae tendineae to the affected mitral valve leaflet(s) in a beating heart. The device is intended to be a Single Use Device, used in a surgical operating suite or equivalent setting. Harpoon Medical has developed a novel small-diameter (< 3 mm) rigid linear delivery system using a needle wrapped with ePTFE in a pre-formed knot configuration. The device delivers replacement chordae using a valved introducer inserted a few centimeters "off apex" using Transoesophageal echocardiography (TOE). To deploy the pre-formed knot on the atrial side, the delivery system is actuated to advance the needle and pre-formed knot through the leaflet. The delivery system then retracts the needle, leaving the pre-formed knot on the atrial side of the leaflet. After deployment, the delivery system is withdrawn from the valved introducer, exposing the replacement chordae tendineae. The procedure may be repeated up to 4 times using a single valved introducer. The replacement chordae tendineae are adjusted under real-time TOE to optimise the surface of coaptation between leaflets before they are secured to an ePTFE pledget on the epicardium.

#### POTENTIAL BENEFITS

It is anticipated, that the Harpoon Medical device will provide advantages over current surgical interventions including: 1) a small minimally invasive incision, 2) no sternotomy, 3) no

cardiopulmonary bypass, 4) no aortic manipulation, 5) a direct path to the valve plane, 6) performed on a beating heart, 7) real-time TOE-guided chordal length adjustment and 8) less complicated procedure that is teachable and adoptable. The only intracardiac implant associated with the Harpoon Medical device is an ePTFE suture, which has a 20+ year history of safety in conventional mitral valve repair procedures. Moreover, the Harpoon approach is unlikely to compromise subsequent traditional open-heart mitral valve repair or replacement procedures.

Conventional mitral valve surgical procedures require a 3 to 6 hour operation with about 7 days (including at least 1 to 3 days in the Intensive Care Unit (ICU)). Recovery after valve surgery may take a long time, depending on how healthy the patient was before the operation. Patients with an office job, can usually go back to work in 4 to 6 weeks. Those who have more physically demanding jobs may need a longer recovery period. It is anticipated that the Harpoon procedure time will be reduced to 1 to 2 hours (average procedure time of 110 minutes) and recovery times would be substantially shorter due to the less invasive nature of the procedure. Collectively, the benefits of the Harpoon procedure should translate into less pain and disability, shorter hospital lengths of stay, fewer strokes, less renal failure, fewer wound infections and lower peri-procedural mortality.

There are alternate treatments available to replace ruptured or elongated chordae tendineae and reduce MR. However, there is no currently effective medical therapy that treats or cures MR, and the alternate procedures to repair the mitral valve are generally more invasive, associated with greater morbidity and/or less effective repair of the mitral valve. The current technologies available to address the structural defects of MR include:

- Open-heart operations to repair or replace the mitral valve. Open cardiac mitral valve operations either require a sternotomy or a thoracotomy, cardiopulmonary bypass, aortic manipulation and cardioplegic cardiac arrest. Mitral valve repair is carried out with leaflet resectional techniques (Carpentier) or nonresectional techniques using ePTFE chordae tendineae placed under direct vision. Because the heart is flaccid and arrested, sizing the chordae tendineae is difficult. Improper sizing of the chordae tendineae may result in a failed or ineffective mitral valve repair. The success of mitral valve repair is significantly dependent on the expertise of the operating surgeon. For patients with degenerative mitral valve disease, mitral valve replacement is inferior to mitral valve repair (short-term higher perioperative mortality and long term substantially higher risks of stroke and prosthetic valve endocarditis as well as either the need for lifelong anticoagulation (mechanical valve) or the risk of repeat mitral operation (bioprosthetic valve)). Mitral valve replacement (compared to repair) is a risk of open cardiac surgery. This procedure is also very invasive and not a feasible option for all patients.
- In 2008, Evalve received a CE mark for the MitraClip in the EU. Shortly thereafter, the company was acquired by Abbott Labs. The implantation of MitraClip does not involve open-heart surgery, but mimics the surgical method of edge-to-edge valve repair where the mitral valve leaflets are clipped together with the device instead of being sutured together. Extensive clinical experience with the MitraClip has been collected over the last six years and the clinical efficacy has been mixed.

 <http://www.rbhh-specialistcare.co.uk/diagnosis-treatments/heart-treatments/valve-repair-or-replacement-incl-tavi-mitral-valve-repair/>

- In 2013, NeoChord released a CE marked, Class III medical device to the EU as a minimally invasive procedure that is performed on a beating heart to replace chordae tendineae that have become elongated or ruptured. NeoChord does not involve open-heart surgery, but mimics the surgical method of suturing the free-edge of the mitral valve to install replacement chordae tendineae. Initial clinical results have been promising, but the device requires the surgeon to enter the left ventricle with a large shaft (~3x larger than the Harpoon device) for every suture. Suture placement is limited to the free edge of the mitral leaflet and requires the operator to grasp a moving mitral leaflet for deployment.

Although these procedures are available to cardiothoracic surgeons in the EU, there is still a need for additional minimally invasive treatment options for patients suffering from MR. Based on the outcomes from the EFS, it is expected that the Harpoon Medical device will be a valuable treatment alternative for patients suffering from MR.

## POTENTIAL RISKS

There are risks associated with our protocol. The Harpoon Medical device received CE Mark in December 2017. The study uses minimally invasive surgical techniques to repair/replace the native chordae in a human heart. The discomforts and risks that we predict are equivalent to what is expected from similar cardiac procedures performed through the chest wall on a beating heart to repair the mitral valve (i.e., localised pain, discomfort at the incision site(s) and the risks of bleeding, injury to the myocardium and injury to the mitral valve). If the Harpoon Medical device does not perform as designed, classical definitive repair of the mitral valve using conventional open-heart procedures and cardiac bypass will be used to facilitate the repair. There may be a possibility that the TRACER procedure causes the classical definitive repair that would be carried out subsequently, if needed making the classic repair more technically and clinically difficult.

#### **IV. STUDY OBJECTIVES**

The purpose of this study is to evaluate the safety and performance of the Harpoon Medical device.

##### **PERFORMANCE GOALS**

**Primary Performance Endpoints:** To demonstrate that the Harpoon Medical device performs as designed and has the ability to successfully implant one or more ePTFE chordae tendineae on the mitral valve via a small left thoracotomy on the beating heart and reduce mitral regurgitation from “severe” to less than or equal to “moderate” at the conclusion of the procedure and at 30 days post-procedure.

**Secondary Performance Endpoints:** Severity of mitral regurgitation at 6 months, 12 months, 18 months, 24 months, 30 months, and 36 months follow-up shall be tracked and recorded.

##### **SAFETY GOALS**

**Primary Safety Endpoints:** Procedure freedom from Serious Adverse Events (SAEs) during the ePTFE implantation procedure, at discharge, and at 30 days follow-up shall be tracked and recorded.

**Secondary Safety Endpoints** Freedom from Serious Adverse Events (SAEs) at 6 months, 12 months, 18 months, 24 months, 30 months and, 36 months follow-up shall be tracked and recorded.

## **V. STUDY DESIGN**

This is a prospective, single arm, nonrandomised, multi-center EU study to demonstrate the performance and safety of the Harpoon Medical device in patients with degenerative MR.

## **VI. STUDY POPULATION**

### NUMBER OF PATIENTS

Up to 20 patients in the UK may be enrolled. The estimated enrollment period is 24 months, and all patients shall be followed for 30 days, 6 months, 12 months, 18 months, 24 months, 30 months, 36 months, 48 months and 60 months after implantation in accordance with the Clinical Investigations schedule provided in Section VIII.

### INTENDED USE

The Harpoon Medical device is intended to be used by a trained medical professional. The device is designed to reduce the degree of mitral regurgitation by delivering and anchoring artificial chordae tendineae to the affected mitral valve leaflet(s) in a beating heart. The device is intended to be a Single Use Device, used in a surgical operating suite or equivalent setting.

### INCLUSION CRITERIA

- Age  $\geq$  18 years
- Patient referred for mitral valve surgery
- Presence severe MR as read on an echocardiographic study performed within 60 days prior to procedure.
- Estimated post-ePTFE chordae tendineae implantation coaptation surface is adequate in the judgment of the operating surgeon and the patient eligibility committee
- Degenerative mitral valve disease
- Patient is able to sign informed consent and able to return for follow-up and is capable of participating in all testing associated with this clinical investigation
- Women of child-bearing potential have a negative pregnancy test

### EXCLUSION CRITERIA

- Age  $<$  18 years
- Infective endocarditis
- Anterior or bileaflet prolapse
- Functional MR
- History of Mediastinal Radiation
- Inflammatory (rheumatic) valve disease
- Requirement for concomitant cardiac surgery (e.g., coronary artery bypass grafting (CABG), aortic valve surgery, etc.)
- Symptomatic coronary artery disease
- Cardiogenic shock at the time of enrollment

- ST segment elevation myocardial infarction requiring intervention within 30 days prior to enrollment
- Evidence of cirrhosis or hepatic synthetic failure
- Pregnancy at the time of enrollment (women of child bearing age should have negative pregnancy within 14 days of surgery)
- Severe pulmonary hypertension (PA systolic pressure > 70 mmHg)
- Previous cardiac surgery, or surgery on the left pleural space
- Left ventricular, atrial or appendage thrombus
- Severely calcified mitral leaflets
- Recent stroke (< 6 months) with permanent impairment
- EuroScore (for mitral valve repair) > 8%
- Patients with contraindications to Transoesophageal echocardiography
- Severe left or right ventricular dysfunction
- NYHA Class IV
- Renal insufficiency CKD stage 3b or worse (GFR < 45 ml/min/1.73 m^2)
- Patient is participating in another clinical study for which follow-up is currently ongoing. (Co-enrollment in an investigational device or interventional study)
- Patient with non-cardiac co-morbidities and life expectancy < 1 year  
Patient has a condition or conditions that, in the opinion of the Investigator, preclude participation, including willingness to comply with all follow-up procedures

#### PATIENT WITHDRAWAL FROM THE STUDY

A withdrawal refers to a patient who is determined to be inactive in the study due to physician discretion, patient or family choice (if the patient becomes incapacitated and is unable to continue with the study due to a family choice), and loss to follow-up or patient death. Final status shall be reported on all patients as per the informed consent. Three documented phone calls and a registered/certified letter shall be used to assure that there is minimal loss to follow-up. If these efforts to contact the patient are unsuccessful, the patient shall be considered lost to follow-up.

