## TREATMENT PROCEDURE/ASSESSMENTS

The procedural approach requires that the patient be administered a general (single lumen) endotracheal anesthesia with appropriate monitoring lines (e.g. arterial line) and heparinised saline to achieve an activated clotting time of  $\geq 350$  seconds. The patient should be placed in the supine position with elevation of the left hemithorax to 30°. Briefly, the procedure consists of performing a small left lateral thoracotomy incision overlying the left ventricular apex, opening the pericardium and selecting an insertion site on the epicardium for the Harpoon Medical device where a monofilament purse-string suture is placed to hold the Harpoon device introducer in place and reduce bleeding. Once the introducer is in place, the device is inserted and positioned adjacent to the mitral leaflet under TOE guidance and bulky suture knot is deployed to secure paired sutures in the leaflet. The paired sutures are brought outside the ventricle. Up to four (4) suture pairs may be placed, using a singled valved introducer, to secure and align apposition between the anterior and posterior mitral leaflets. If more than four (4) suture pairs are required, the valved introducer must be removed and reinserted for reuse, and then an additional four (4) suture pairs may be inserted. Once an adequate number of suture pairs are placed, the device and introducer are removed, and the suture pairs are tightened and secured to the exterior myocardium using pledges for each suture pair. The thoracotomy should be closed, and chest tube(s) should be inserted, per hospital standard of care.

The details of the procedure are described thoroughly in the Harpoon Medical device Instructions for Use.

If in the judgment of the operating surgeon, adequate MR reduction has not been achieved, or if for any other clinical reason, conversion to SOC mitral valve surgery via a median sternotomy shall be performed. This procedure may be performed at the time of the Harpoon Medical TRACER procedure or at a later date/time at the discretion of the operating surgeon. Subjects who undergo a conversion to SOC mitral valve surgery via a median sternotomy will be followed up for 30 days.

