## FOLLOW-UP PROCEDURES/ASSESSMENTS

**Post-procedure management:** Standard hospital protocols for the management of patients after mitral valve surgery shall be followed. Unless other indications for anticoagulation are present, all patients shall receive only 325 mg/day, beginning on arrival to the intensive care unit).

**Discharge:** All patients shall be discharged from the hospital at the discretion of the attending cardiac surgeon. Prior to dismissal all patients shall undergo a comprehensive pre-dismissal TOE, as well as a physical assessment (vide supra) in accordance with the schedule of Clinical Investigations.

**Patient follow-up:** Patients shall be seen in the outpatient clinic 30 days (+10 days/-0 days) after the Harpoon procedure. A TTE and a clinical assessment shall be performed at that time (in accordance with the schedule of Clinical Investigations) to evaluate the device against the primary and secondary performance and safety endpoints.

Additional clinical and TTE follow-up in a registry fashion shall occur for all active subjects (in accordance with the Clinical Investigations defined in the table below) at the following intervals:

- 6 months (+/- 30 days),
- 12 months (+/- 30 days)
- 18 months (+/- 30 days)
- 24 months (+/- 30 days)
- 30 months (+/- 30 days)
- 36 months (+/- 30 days)
- 48 months (+/- 30 days) and
- 60 months (+/- 30 days)

If due to an increase of MR, or due to any other medical circumstances, and a study patient has to undergo a Mitral Valve reoperation, this patient will be followed up by the study team for 30 days and then will be exited from the study

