Freedom from Serious Adverse Events (SAEs) during the ePTFE implantation procedure, at discharge, and at 30 days follow-up will be tabulated. The number of patients experiencing one or more AEs or SAEs at 30-days post-procedure, the percentage of patients, and the exact 95% confidence limit will be calculated. Patients who die prior to 30 days will be considered failures for this analysis.

Freedom from Serious Adverse Events (SAEs) at 6 months, 12 months, 18 months, 24 months, 30 months and 36 months follow-up shall be tabulated. The number of patients experiencing one or more AEs or SAEs at 6 months, 12 months, 18 months, 24 months, 30 months, 36 months, 48 months and 60 months follow-up, the percentage of patients, and the exact 95% confidence limit will be calculated.

These data shall be used to assess the safety and performance of the Harpoon Medical device, and are not designed to test a statistical hypothesis, and therefore a formal sample size has not been calculated. All data shall be captured on an intent-to-treat basis. Data shall be reported as descriptive statistics.

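### Discretionary, reoperation and conversion exits end data collection on a one-time implant, and no death or missing-data rule covers the results from 6 to 60 months

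*Combined protocol and SAP*

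**What the plan says.** **Who leaves.** Section VI (Patient withdrawal from the study) states: "A withdrawal refers to a patient who is determined to be inactive in the study due to physician discretion, patient or family choice". The same sentence continues to "and loss to follow-up or patient death". No condition is attached to the physician's decision. The clause then adds: "Final status shall be reported on all patients as per the informed consent". It does not say what final status contains.

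**Who stays.** Section VII (Follow-up procedures/assessments) says of the period after the 30-day visit: "Additional clinical and TTE follow-up in a registry fashion shall occur for all active subjects". For a patient who has a mitral reoperation, "this patient will be followed up by the study team for 30 days and then will be exited from the study". Under Treatment procedure/assessments, patients converted to standard mitral surgery "will be followed up for 30 days".

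**What is promised.** Section VI (Number of patients) and Section X both schedule every patient for visits to 60 months. Section X also states: "All data shall be captured on an intent-to-treat basis". It does not define the term or give a denominator for any late visit.

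**Which rules exist.** In Section X, a death before the 30-day evaluation or a failed procedure is a failure for the primary performance analysis. Other losses are carried forward from the procedure to 30 days, with a tipping-point analysis. For safety, a death before 30 days is a failure. Section X then plans MR percentages to five years and SAE counts to 60 months, with no corresponding rule.

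**The treatment.** Section III (Potential benefits) says: "The only intracardiac implant associated with the Harpoon Medical device is an ePTFE suture". It is placed once.

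**The concern.** In a drug trial, a discretionary withdrawal may end an exposure. Here nothing is left to stop once the chords are in place, so making a patient inactive ends visits and echocardiograms and nothing else. The plan does not separate ending visits from ending data collection.

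The exits can also depend on outcome. Reoperation and conversion are tied directly to how the repair performed. A physician's decision may be tied to the patient's condition, and the text neither excludes this nor asks for a criterion. If patients with recurrent MR leave more often than others, a late success rate among those still seen will be too high. Analysis can bound that error but cannot remove it, because the data were never collected.

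At stake are the MR grades and SAE results from 6 to 60 months. The present amendment exists to extend follow-up to five years, so this is the evidence it is meant to produce.

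**Working it through.** **1. What happens to a patient who leaves after 30 days**

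| Exit route | Follow-up under the plan | Rule for late MR or SAE results |
|---|---|---|
| Physician discretion | ends (no longer active) | none |
| Patient or family choice | ends | none |
| Loss to follow-up | ends after contact attempts | none |
| Reoperation | 30 days, then exit | none |
| Conversion to standard surgery | 30 days | none late; a failed procedure is a failure at 30 days |
| Death | classed as withdrawal | none late; a failure only if before 30 days |

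The universal schedule to 60 months and the restriction to active subjects give different answers for the first five routes. The intent-to-treat sentence does not settle which applies, because it concerns how data are captured and supplies no value where no echocardiogram was done.

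**2. How much a late rate can move**

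The plan gives no late attrition figure to reproduce and no count for any route, so only bounds are possible. Let N be the patients in the set, k the number unobserved at a late visit, and s the successes among those observed.

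- Rate among those observed: s/(N − k)
- Lower bound on all N (every unobserved patient a failure): s/N
- Upper bound on all N (every unobserved patient a success): (s + k)/N
- Width of the band: k/N

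N = 30 is the set in Section X that supports the CE mark. The values of k, and an observed rate near 85%, are assumptions. The plan's only allowance for loss is 30 − 26 = 4 patients; it was made for the 30-day endpoint and serves here only as a reference point.

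| k | Observed only | Lower bound, all 30 | Upper bound, all 30 | Width |
|---|---|---|---|---|
| 1 | 25/29 = 86.2% | 25/30 = 83.3% | 26/30 = 86.7% | 3.3 points |
| 3 | 23/27 = 85.2% | 23/30 = 76.7% | 26/30 = 86.7% | 10.0 points |
| 4 | 22/26 = 84.6% | 22/30 = 73.3% | 26/30 = 86.7% | 13.3 points |
| 6 | 20/24 = 83.3% | 20/30 = 66.7% | 26/30 = 86.7% | 20.0 points |

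**3. The unfavourable case, as an illustration**

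Assume 24 of 30 patients truly have moderate or less MR at five years: 24/30 = 80%. If 3 of the 6 failures have left, the observed rate is 24/27 = 88.9%. If 5 have left, it is 24/25 = 96%.

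The study summary allows up to 20 patients in each of up to four countries, so the set could reach 4 × 20 = 80. One unobserved patient then adds 1/80 = 1.25 points. With 64/80 = 80% true success, losing 3 or 5 failures gives 64/77 = 83.1% or 64/75 = 85.3%. The direction is the same and the shift is smaller.

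**The case against.** Four stronger readings are tempting, and the documents do not support them.

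- **Late results describe a group chosen by physicians.** This is possible but not shown. Discretion is one route among several, no counts are given, and the clause does not say which physician decides. Source Documentation in Section XI already requires the reason for discontinuation in the medical record.
- **Classing death as withdrawal hides it.** Death meets the SAE definition in Section VIII and is a status on the event report, and AEs are monitored to 60 months. Deaths before 30 days are failures for both primary endpoints. What remains unclear is how a later death enters an MR denominator.
- **The primary analysis is compromised.** It is not. The 30-day endpoint has its own death, carry-forward and tipping-point rules.
- **The plan flatly contradicts itself.** A visit schedule and a withdrawal clause normally coexist, and active may mean only those not dead, withdrawn or exited. Nor do the documents say that late percentages use active patients as the denominator.

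It is also fair to say that the late results are secondary and descriptive, that the illustrations rest on assumed counts, and that the consent pages are not available, so existing permission for record access cannot be judged. Serious device effects still ongoing are followed to outcome under Section VIII.

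All of this limits the point without answering it. None of these provisions requires an MR grade, a reintervention check or a search for new SAEs once a patient is inactive. AE monitoring runs to a 60-month visit that an inactive patient does not have. Committee adjudication stops at 36 months.

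**Conclusion.** The concern holds in limited form, and the text should be changed. The plan allows exits that stop no exposure, may depend on outcome, and end collection of MR and SAE data. It has no rule for deaths or missing data after 30 days. The failure-linked routes that the text spells out are reoperation and conversion; physician discretion is an open-ended third.

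The size is unknown. If the set is 30, each unobserved patient adds 3.3 points of uncertainty to a late rate, and four would add 13.3. Overstatement of late success requires that failures leave more often than successes and that the reported rate uses only those observed; the documents establish neither. The 30-day primary conclusion stands apart from this, and deaths remain in the SAE results.

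**What to change.** Reconcile Section VI (Number of patients; Patient withdrawal) with Section VII (Treatment procedure; Follow-up procedures) as follows.

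1. Limit withdrawal from data collection to withdrawal of consent, including a family decision for an incapacitated patient.
2. Treat exits by physician decision, after reoperation and after conversion as *visits stopped*. Collect vital status, mitral reintervention and SAEs from medical records to 60 months, within the consent given.
3. Record death as an outcome, not a withdrawal.
4. In Section X, report the number of patients and their last MR grade by exit route. State the denominator at each late visit and how death and reoperation are counted. Show late MR rates on all implanted patients, with worst-case and best-case bounds, beside the rates in those observed.

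**Cost.** Amendment wording, an ethics submission, possible re-consent, and occasional record checks for a few patients. No visits or procedures are added. Section VIII (Retrospective collection of data) already plans to re-contact patients for consent, so the request can go with it. Data from patients who left earlier may not be recoverable; for them the table of exits and the bounds are what remains.
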